As a general rule the following will be reviewed to provide a guide to safety decisions:

Unacceptable toxicities will be defined as follows (based on NCI Criteria for Adverse Events (CTCAE) (v4.03: June 14, 2010) for reactions considered related to TG02 and/or GM-CSF:

- Injection site reaction of \geq grade 3 (grade 3: Ulceration or necrosis; severe tissue damage; operative intervention indicated, grade 4: Life-threatening consequences; urgent intervention indicated, grade 5: death).
- Other relevant clinically significant toxicity \geq grade 3 (excluding treatable nausea and vomiting). However for certain toxicities such as laboratory assessments without a clear clinical correlate, a discussion in the SSC may take place to evaluate if this AE should be assessed as DLT.
- \geq Grade 3 'allergic reaction/anaphylactic reaction' in spite of prophylaxis with antihistamine and steroids.

All AEs and SAEs will be reviewed and will also be compared to those of the precursor vaccine TG01 (see Investigator's Brochure).

If more than 1 out of the 3 patients has DLT the SSC will review the nature of the events and make a final decision if the rest of the patients may be enrolled.

When all safety data, systemic immune responses (Delayed-Type Hypersensitivity (DTHs)) and tumour material (analysed for intra-tumoural T cells infiltration) are available for all patients in Part I of the study, the Safety Steering Committee will evaluate the data to assess safety and preliminary immune activity and efficacy to make a recommendation whether the study will proceed or not to Part II of this protocol. In Part II 10 new patients, not previously treated with TG02, will be recruited. No patients treated in Part I will be treated in Part II. The SSC's recommendation will form the basis for sponsor to make a final decision.

Part II

At the discretion of the sponsor, a decision will be made to initiate Part II of the study where up to 10 patients will be treated with TG02-treatment plus pembrolizumab for up to 10 weeks (up to 6 TG02-treatments) prior to surgery. The first 3 patients will be enrolled in a sequential manner with a minimum lag time of 6 weeks between dosing of the first 3 subjects to ensure an acceptable safety profile.

The safety data collected during the first 6 weeks for the 3 first patients will be reviewed by the SSC in a similar manner as in Part I, as TG02-treatment in combination with pembrolizumab is a novel treatment.

Schedule of events:

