4.8. Rationale for dose regimen

TG02

TG02 given in the TG02-treatment will be administered to the patient at week 1, 2, 3, 4, and 6. If surgery is scheduled after week 10 one more TG02-treatment will be given in week 10. In addition to this TG02 will at certain time points (week 1, week 4, week 6, week 8 and possible week 10), be administered intradermally (without prior administration of GM-CSF) as a DTH test to evaluate the immunological response. The rationale for this regimen is based on the results from the previous and ongoing studies with TG01/GM-CSF that demonstrate that prevailing RAS mutation specific T cells responses are induced in cancer patients after 4-6 weeks of vaccination.

Pembrolizumab

Although the licensed dosing regimen for pembrolizumab is 3-weekly, in this window of opportunity study there is limited time between the start of TG02 vaccinations and surgery. Also, in order that the scheduling of study visits can be minimised to avoid extra patient visits, it is proposed to administer the pembrolizumab 2-weekly. Based on the data reported from the KEYNOTE 006 study for melanoma (Schachter 2017), the efficacy was similar between the 2-weekly and 3-weekly schedule with very similar safety profiles. Additionally, time needs to be allowed for a TG02 specific immune response to be induced; therefore, pembrolizumab will be started at week 4 and continued two-weekly until surgery

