- 6: If surgery is scheduled after Day50/Week 8, pembrolizumab will be given at Day 50/Week 8. If surgery scheduled after Day 64/Week 10, a further pembrolizumab infusion will be given at Day 64/Week 10.

Part I

Approximately 4-6 patients diagnosed with locally advanced primary and recurrent colorectal cancer will be given TG02-treatment for up to 10 weeks (up to 6 TG02-treatments) prior to surgery.

TG02 is an eight peptide vaccine. Significant clinical data exists for its precursor vaccine, TG01, which contains 7 of the 8 mutant RAS peptides present in TG02. TG01 in combination with GM-CSF has been shown to be immunogenic and well tolerated up to 11 weeks of treatment.

Since one of the eight peptides in TG02 has not previously been administered to humans, the first 3 patients will be enrolled in a sequential manner with a minimum lag time of 4 weeks between dosing of the first 3 subjects to ensure an acceptable safety profile.

The safety data collected during the first 4 weeks for the three first patients will be reviewed by a SSC consisting of Sponsor representatives, the Principal Investigator, relevant Sub-Investigators and one Independent Physician.

As a general rule the following will be reviewed to provide a guide to safety decisions:

Unacceptable toxicities will be defined as follows (based on NCI Criteria for Adverse Events (CTCAE) (v4.03: June 14, 2010) for reactions considered related to TG02 and/or GM-CSF:

- Injection site reaction of \geq grade 3 (grade 3: Ulceration or necrosis; severe tissue damage; operative intervention indicated, grade 4: Life-threatening consequences; urgent intervention indicated, grade 5: death).
- Other relevant clinically significant toxicity \geq grade 3 (excluding treatable nausea and vomiting). However, for certain toxicities such as laboratory assessments without a clear clinical correlate, a discussion in the SSC may take place to evaluate if this AE should be assessed as DLT.
- \geq Grade 3 'allergic reaction/anaphylactic reaction' in spite of prophylaxis with antihistamine and steroids.

All AEs and SAEs will be reviewed and will also be compared to those of the precursor vaccine TG01 (see Investigator's Brochure).

If more than 1 out of the 3 patients has DLT the SSC will review the nature of the events and make a final decision if the rest of the patients may be enrolled.

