When all safety data, systemic immune responses (DTHs) and tumour material (analysed for intra-tumoural T cells infiltration) are available for all patients in Part I of the study, the sponsor, with input from the Steering Committee, will evaluate the data to assess safety and preliminary immune activity and efficacy to make the decision to proceed or not to Part II of this protocol. In Part II up to 10 new patients, not previously treated with TG02, will be recruited. No patients treated in Part I will be treated in Part II.

The SSC will review the tolerability of TG02-treatment in accordance with the SSC charter and this review will be based on an assessment of adverse events, laboratory

findings and, in particular the occurrence of hypersensitivity reactions. Toxicity grading will use NCI CTCAE version 4.03.

Part II

Up to 10 patients will be treated with TG02-treatment plus pembrolizumab for up to 10 weeks (up to six TG02-treatments and up to 4 pembrolizumab infusions) prior to surgery.

Again, since one of the eight peptides in TG02 is first in human, and that the use of pembrolizumab will be in a novel setting, as a precaution, the combination of TG02-treatment and pembrolizumab will be initiated first in 3 patients and evaluated for safety prior to subsequent recruitment of patients according to the same procedure as described above for Part I. The first 3 patients will be enrolled in a sequential manner with a minimum lag time of 6 weeks between dosing of the first 3 subjects to ensure an acceptable safety profile. The safety data collected during the first 6 weeks for the 3 first patients will be reviewed by the SSC.

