3 STUDY OBJECTIVES AND DESIGN

3.1 Study Objectives

The primary objectives of the study are:

- To determine the safety of TG02-treatment (Part I) in combination with pembrolizumab (Part II)
- To evaluate the systemic TG02-specific immune responses and to investigate tumour T cell infiltration in tumour specimens

The secondary objectives of the study are:

- To investigate changes in immunological and pathological markers in tumour tissue
- To investigate changes in fluorodeoxyglucose (FDG) positron emission tomography – computed tomography (PET-CT) images
- To investigate changes in carcinoembryonic antigen (CEA)

The exploratory objectives of the study are:

- To investigate changes in circulating tumour cells and/or circulating tumour DNA (ctDNA)
- To investigate the functionality of rat sarcoma (RAS) mutation specific T cells in tumour tissue and peripheral blood

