3.2 Study Design

This is a non-randomised, open label Phase Ib exploratory study to investigate the safety of and immune responses to TG02-treatment, first as monotherapy (Part I) and thereafter as combination therapy with pembrolizumab (Part II) in patients with locally advanced primary and recurrent RAS mutant colorectal cancer eligible for radical pelvic surgery at time of enrolment.

Part I

Approximately 4-6 patients diagnosed with locally advanced and recurrent RAS mutant colorectal cancer will be given TG02-treatment for up to 10 weeks (up to six TG02 treatments; week 1, 2, 3, 4, 6 and 10 if surgery occurs beyond week 10) prior to surgery.

TG02 is an eight-peptide vaccine. Significant clinical data exist for its precursor vaccine, TG01, which contains 7 of the 8 mutant RAS peptides present in TG02. TG01 in combination with granulocyte macrophage colony stimulating factor (GM-CSF) has been shown to be immunogenic and well tolerated up to 11 weeks of treatment.

Since one of the eight peptides in TG02 has not previously been administered to humans, the first 3 patients will be enrolled in a sequential manner with a minimum lag time of 4 weeks between dosing of the first 3 patients to ensure an acceptable safety profile.

The safety data collected during the first 4 weeks for the first 3 patients will be reviewed by a safety steering committee (SSC) consisting of Sponsor representatives, the Principal Investigator, relevant Sub-Investigators and one Independent Physician.

As a general rule the following will be reviewed to provide a guide to safety decisions:

Unacceptable toxicities will be defined as follows (based on National Cancer Institute Criteria for Adverse Events (NCI CTCAE) v4.03: June 14, 2010) for reactions considered to be related to TG02 and/or GM-CSF:

- Injection site reaction of \geq grade 3 (grade 3: ulceration or necrosis, severe tissue damage, operative intervention indicated, grade 4: life-threatening consequences, urgent intervention indicated, grade 5: death)
- Other relevant clinically significant toxicity \geq grade 3 (excluding treatable nausea and vomiting). However, for certain toxicities such as laboratory assessments without a clear clinical correlate, a discussion in the SSC may take place to evaluate if this adverse event (AE) should be assessed as a dose limiting toxicity (DLT).

- \geq Grade 3 'allergic reaction/anaphylactic reaction' in spite of prophylaxis with antihistamine and steroids

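### The Part II run-in borrows a DLT definition from Part I that does not count toxicity attributed to pembrolizumab alone

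*Protocol*

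**What the plan says.** Protocol 6.2 lists the unacceptable toxicities under Part I. They are injection site reactions of grade 3 or higher, other clinically significant toxicity of grade 3 or higher, and allergic reactions of grade 3 or higher despite prophylaxis. The list applies "for reactions considered related to TG02 and/or GM-CSF". The synopsis has the same wording, and SAP 3.2 has "for reactions considered to be related to TG02 and/or GM-CSF". If more than one of the three patients has a DLT, the SSC reviews the events and decides whether enrolment may go on.

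For Part II, protocol 6.2 gives two reasons for a cautious start. One TG02 peptide is new to humans, and "the use of pembrolizumab will be in a novel setting". Three patients are treated first and "evaluated for safety prior to subsequent recruitment of patients", "according to the same procedure as described above for Part I". In the synopsis, the six-week safety data "will be reviewed by the SSC in a similar manner as in Part I"; SAP 3.2 says the same. No separate Part II definition is given.

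Protocol 4.8 explains why pembrolizumab is given every two weeks: "Although the licensed dosing regimen for pembrolizumab is 3-weekly". SAP 3.1 words the Part II safety objective for the combination. SAP 5.2 has relatedness assessed separately for TG02, GM-CSF and pembrolizumab, and plans a table of events related to pembrolizumab only.

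**The concern.** The run-in exists partly because pembrolizumab is being added, on a schedule tighter than the licensed one. Yet the criterion it inherits counts only events linked to the vaccine and its adjuvant. Pembrolizumab is not given in Part I, so the restriction does no harm there. Carried into Part II, it leaves out events attributed solely to the added drug, which the SAP already plans to tabulate.

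Read literally, the run-in could yield no DLTs after a grade 3 to 5 event attributed to pembrolizumab. The criterion would then say nothing about that event when the SSC considers treating up to 10 − 3 = 7 further patients who are waiting for planned surgery.

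**Working it through.** **Text.** What differs between the two parts, and what does not:

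| Item | Part I | Part II |
|---|---|---|
| Products | TG02, GM-CSF | TG02, GM-CSF, pembrolizumab |
| Lag and review period | 4 weeks | 6 weeks |
| Run-in size | 3 | 3 |
| Attribution needed for a DLT | TG02 and/or GM-CSF | none stated; Part I by reference |
| SSC criterion | more than 1 of 3 | none stated; Part I by reference |

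The period was changed for Part II and the attribution was not. The documents use the term DLT without defining it; I take it to mean the listed unacceptable toxicities, which is the natural reading.

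**Size.** The documents state no DLT rate or operating characteristic, so there is no figure to reproduce. All rates below are assumptions, with independence between patients and between the two kinds of event:

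- n = 3 (protocol 6.2, Part II).
- a = chance that a patient has a qualifying event related to TG02 and/or GM-CSF; 5% or 10% assumed.
- b = chance that a patient has a qualifying event attributed to pembrolizumab alone; 5%, 10% or 20% assumed. It applies to the review window only. With the first infusion on Day 22 and review at six weeks (Day 42), that is about 20 days.

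Step 1. At least one pembrolizumab-only event among three patients: 1 − (1 − b)³ = 14.3%, 27.1%, 48.8% for b = 5%, 10%, 20%.

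Step 2. No counted DLT although such an event occurred: (1 − a)³ × [1 − (1 − b)³]. For a = 5% and b = 10% this is 0.8574 × 0.2710 = 23.2%.

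Step 3. Criterion met (two or more of three): 3q²(1 − q) + q³. As written, q = a. With pembrolizumab included, q = 1 − (1 − a)(1 − b). For a = 5% as written: 3 × 0.0025 × 0.95 + 0.000125 = 0.7%.

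| a | b | Step 2 | Criterion met, as written | q with pembrolizumab | Criterion met, with pembrolizumab |
|---|---|---|---|---|---|
| 5% | 5% | 12.2% | 0.7% | 9.75% | 2.7% |
| 5% | 10% | 23.2% | 0.7% | 14.5% | 5.7% |
| 5% | 20% | 41.8% | 0.7% | 24.0% | 14.5% |
| 10% | 5% | 10.4% | 2.8% | 14.5% | 5.7% |
| 10% | 10% | 19.8% | 2.8% | 19.0% | 9.5% |
| 10% | 20% | 35.6% | 2.8% | 28.0% | 19.1% |

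Step 4. Cross-check from a total rate. Suppose the combination causes qualifying toxicity in 20%, 30% or 40% of patients, half of it attributed to pembrolizumab alone. The criterion is then met with probability 2.8%, 6.1% or 10.4% as written, against 10.4%, 21.6% or 35.2% with pembrolizumab included. If all of it is attributed to pembrolizumab alone, the probability as written is zero.

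**The case against.** The strongest reply is that little turns on the criterion. It does not stop enrolment; it leads to an SSC review and decision, and the SSC reviews the run-in anyway. Protocol 6.2 calls the list a guide, has all adverse events reviewed, and holds recruitment after the third patient for safety evaluation. Protocol 13.5 has the SSC look at each of the first three patients and consider all available data. This stands, and it limits the point to what counts as a DLT.

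Second, reviewing Part II in a similar manner need not mean word for word, and the longer window shows adaptation to pembrolizumab. That is fair, but no text supplies another attribution rule. The SSC text in 6.2 and 13.5 also singles out the safety of TG02-treatment.

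Third, the excluded category may be small. In the six-week window both infusions (Days 22 and 36) fall on TG02/GM-CSF days, and Appendix II lets timing alone support a reasonable possibility and treats ambiguous cases as related. Events judged related to both pembrolizumab and the vaccine or adjuvant therefore still count. But Appendix II also denies a reasonable possibility where another cause is more likely, and it names other drugs among alternative causes. An event typical of pembrolizumab could be classified that way.

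Fourth, the SSC charter was not available and may already cover this. That stands.

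Two stronger readings do not hold. A reader might infer that pembrolizumab-only events escape review; the provisions above show otherwise. A reader might also infer that a single DLT has no bearing on enrolment. Protocol 13.5 lets recruitment continue only if there are no safety concerns, 6.2 holds recruitment whatever the count, and 7.5 allows the study to be stopped for new or unexpectedly frequent events. Asking for a lower trigger would be a preference, not the repair of an error.

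**Conclusion.** The point holds as a gap in definition. The stated toxicity criterion for the Part II run-in does not count grade 3 or higher events attributed to pembrolizumab alone, although pembrolizumab is a stated reason for the run-in. The SSC would see such events and could act on them.

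Under the assumed rates, a run-in has no counted DLT despite at least one pembrolizumab-only event with probability 10.4% to 41.8%. Including pembrolizumab raises the chance of meeting the criterion from 0.7% to between 2.7% and 14.5% at a = 5%, and from 2.8% to between 5.7% and 19.1% at a = 10%. These figures show scale only. Nothing in the documents supports a particular rate, and the upper values of b may be high for a window of about 20 days. The conclusion also assumes that Part II takes over the Part I definition unchanged and that the charter does not already extend it.

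**What to change.** In the Part II text of the synopsis, protocol 6.2 and SAP 3.2, add: *For Part II, unacceptable toxicity (DLT) is any toxicity meeting the criteria above that is considered related to TG02, GM-CSF and/or pembrolizumab.* Align the SSC charter. Keep the criterion of more than one DLT in three patients.

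The cost is a small protocol amendment, notified to the ethics committee under protocol 13.1, and a somewhat higher chance that the criterion is reached, as tabulated above. Reaching it still means an SSC decision, not an automatic stop. No new data collection is needed. If the charter already contains this rule, the edit only brings the protocol and SAP into line with it.

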6.3. Study Duration

The total duration of the study is expected to be 2.5 years, approximately 15 months for Part I and 15 months for Part II. The total duration of the study will be dependent on whether the study proceeds to Part II or not.

The patient will be in the study for a maximum of 20 weeks. The treatment period will be up to 10 weeks, dependent on the timing of scheduled surgery. The patient will be followed up to 6 weeks after surgery.

6.4. Study Visit Schedule

The schedule of visits (Table 6-1, Schedule of visits) reflects the assessments that will occur during the study, i.e. screening period, treatment period, and end of study. Patients will be screened for the study over a period of 14 days. The TG02-treatment period will be up to maximum 10 weeks and the end of study visit will be approximately 6 weeks after surgery.

- Weekly visits should occur within a window of ± 2 days.
- Two weekly visits should occur within a window of ± 4 days.
- End of study visit (EOS) should occur within 6 weeks after surgery.

Surgery should occur between week 8 and 14, if not postponed due to some unforeseen reasons, which will be documented. If for any reason, the patient will not have surgery, a biopsy will be obtained at the time of planned surgery if possible.

All trial treatment-related toxicities and SAEs must be followed until resolution unless, in the investigator's opinion, the condition is unlikely to resolve because of the patient's underlying disease.

6.4.1. Screening Period

Before initiating any screening activities, the scope of the study should be explained to each patient. Patients should be advised of any known risks inherent in the planned procedures, of any alternative treatment options, of their right to withdraw from the study at any time for any reason, and of their right to privacy. After this explanation, patients should be asked to sign an EC approved statement of informed consent.

The screening visit will determine patient eligibility according to the inclusion/exclusion criteria (section 7.3 and 7.4). The following assessments will be performed during this period:

- Demographics and medical history (including detailed information about medical history of colorectal cancer and previous treatments)
- Medication and treatment history and concomitant medication (including medication taken in the 4 weeks before screening period, relevant information should be captured in the CRF)
- Urine or serum pregnancy test (for women of childbearing potential)
- Physical exam (review of the major body systems, vital signs (height, weight, heart rate, blood pressure, tympanic body temperature))
- 12-lead ECG evaluation
- ECOG Performance status
- Blood samples for routine haematology, serum biochemistry and CEA biomarker (Table 6-1)
- FDG PET-CT scan for tumour assessment of standard uptake value (SUV-max) as close as possible to first visit (should be within the last 4 weeks prior to first TG02-treatment)
- For patients receiving chemo-radiation before enrolment into study, core biopsy of target colorectal tumour should be taken after chemo-radiation and during the screening window (2 week) and as close as possible to the first TG02-treatment (day 1, week 1). For patients not having chemo-radiation before enrolment into the study, a core biopsy of target colorectal tumour can be taken within the last 4 weeks but as close as possible to the first TG02-treatment (day 1, week 1). If a pre TG02-treatment biopsy has been taken for diagnostic workup as hospital procedure, this biopsy, if adequate for the study specific immune analysis and no intervening treatment has been given, can also be used.
- Diagnostic CT/MRI scan according to hospital practice

6.4.2. Treatment period (before surgery):

The treatment period will be from Day 1 (Week 1) and up to surgery, which is planned for week 8 but can occur in a window up to week 14. The following assessments will be performed on Day 1, Day 8, Day 15, Day 22, Day 36, Day 50 and if surgery is after week 10 (Day 64):

- Vital signs (heart rate, blood pressure and tympanic body temperature) and ECOG performance status
- Concomitant medications and adverse events will be monitored continuously
- Physical examination, haematology and serum biochemistry (Table 9-1) before treatment (Day 1) and during treatment on Day 15, Day 36, Day 50 and if surgery after week 10 (Day 64).
- TG02 treatment will be administered on Days 1, 8, 15, 22 and 36. If surgery after week 10 TG02 treatment will also be given at week 10 (Day 64).
- Pembrolizumab will be given on Days 22 and 36. If surgery is scheduled after Day 50/Week 8, pembrolizumab will be given at Day 50/Week 8. If surgery scheduled after Day 64/Week 10, a further pembrolizumab infusion will be given at Day 64/Week 10.
- DTH tests will be performed at baseline (Day 1), week 4 (Day 22), week 6 (Day 36) and week 8 (Day 50) (if surgery is scheduled for week 8 the DTH test should be performed two days before surgery). If surgery is after week 10, and the patient has had negative DTH tests up to and including week 8, an additional DTH test should be performed at week 10 (Day 64).

- Blood samples for in vitro assessment of TG02-specific immune responses (Immunology sample, PBMC) will be taken at baseline (Day 1) and Day 50. If surgery is after week 10, an additional sample should be taken as close as possible up to the date of surgery (see separate Immune monitoring plan).
- The CEA biomarker will be evaluated at Day 50. If surgery is after week 10 a third sample will be taken at Day 64 or just prior to surgery, whichever is the more appropriate.
- Tumour samples for assessment of immune response will be taken at time of surgery. If for any reason the patient will not have surgery a biopsy will be obtained if possible at the latest by week 14 (see separate Immune monitoring plan).
- FDG PET-CT scan for tumour assessment of standard uptake value (SUV-max) as close as possible up to date of surgery.
- Circulating Tumour Cells (CTC) will be evaluated at Day 1 and Day 50. If surgery is after week 10, an additional sample can be taken as close as possible up to the date of surgery.

Additional monitoring during the first 2 hours after any TG02-treatment:

Following any TG02-treatment patients will be monitored for signs and symptoms of hypersensitivity as well as heart rate and blood pressure. A finger pulsometer or similar should be used to monitor heart rate for the first 30 minutes and blood pressure should be measured at 5 and 10 and 30 minutes and then every 30 minutes for up to 2 hours post administration. Additional blood pressure measures should be taken if the patient experiences any of the following: dizziness, feeling cold or clammy, sweating, tingling in the mouth/tongue, itchy palms, feeling lightheaded, abdominal pain or breathlessness.

Measures in case of anaphylaxis should follow the hospital policy and include the availability of intravenous access, oxygen, adrenaline and hydrocortisone.

The administration of TG02 and post-treatment monitoring will occur in the Chemotherapy Treatment Unit or equivalent unit for each the institution with the patient sitting in an appropriate treatment chair or similar.

